While evidence from previous studies in social care as well as Foundation's feasibility studies suggests use of a fully qualified psychotherapist is important to embedding systemic practice, Foundation's scoping reports and feedback from the pilot delivery partner, IFT, highlighted the challenges in recruiting qualified clinicians.

As a result, local authorities will be encouraged to recruit systemic practitioners who are Intermediate Level trained in Systemic Practice⁴³ (who have at least 2 years of training: Foundation year 1, Intermediate year 2,) and offer them the qualifying level Masters training in Family and Systemic Psychotherapy, rather than recruiting practitioners qualified at that level. It is hoped that this will increase the pool of potential applicants, the chances that those recruited will have backgrounds in early help and support recruitment, retention, and sustainability. This has been a successful model used in several areas where IFT has delivered training. IFT and Coram will advise local authorities on job descriptions, key responsibilities, and professional standards to ensure good practice is consistently used across local authorities.

In each intervention local authority systemic practitioners will work with keyworker teams to embed systemic practice alongside keyworker Systemic Champions. The Systemic Practitioners will attend and support IFT training to local authorities, in addition to providing their own informal learning sessions with keyworkers on specific topics of interest after the five days of formal training. For example, how systemic practice can support school-based avoidance, or use of circular questioning and reflectivity to increase quality practice and engagement with families. Systemic practitioners will facilitate monthly group reflective practice sessions, provide 121 consultations to key workers, support the use of systemic tools (such as genograms and family trees) and outcome measures, as well as keyworker engagement and use of the virtual hub.

Systemic practitioners will be line managed with local authorities but have monthly clinical supervision with IFT's Systemic Psychotherapist Delivery Lead. Systemic practitioners will also come together as a group for their own monthly reflective practice meeting run by IFT's Systemic Psychotherapist Delivery Lead to discuss barriers and enablers to the ongoing embedding of systemic practice as well as consistency and fidelity across areas.

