- 2) *missing at random* (data is not randomly distributed but they are accounted for by other observed variables), or
- 3) *missing not at random* (data systematically differs from the observed values) and adjust our approach to analysis based on this assessment.

Where data is missing completely at random, no imputation will be carried out and only available cases will be analysed. Where data is missing at random it will be considered whether multiple imputation is required. Where data is missing not at random it will be considered which sensitivity analyses are required to produce estimates that adjust for missingness.

We anticipate all variables will be analysed using a three-level multilevel modelling approach for family-based outcomes, and two-level multilevel modelling approach for keyworker outcomes to estimate the average effect of the treatment allocation using a Huber-White (HW) robust error procedure to account for heteroscedasticity. We anticipate including fixed effects for delivery site and time from randomisation (to account for ongoing referral throughout the pilot). We will also adjust for stratification factors used at randomisation and report ICCs for clustering. The coefficient will be an estimate of the size and direction of the treatment effect and its significance will be tested with a two-tailed 5% Type I error threshold.

The analysis explore the influence of trial arm allocation compliance using Complier Average Causal Effect Analysis, by including intervention receipt in an instrumental variable analysis. The analysis will also include an exploratory analysis with sub-groups or other exploratory analysis including analysis of harms.

All analysis will adhere to good spreadsheet design principles and document the sequence of steps used to get from raw data to findings to enable review. All data cleaning and analysis will be undertaken in R statistical software. All code and analysis will be quality assured by a second member of staff and includes both the logic and the arithmetic of analysis. Full records of code will be shared with the DfE and published to enable replication.

Implementation and process evaluation

The aim of the Implementation and process evaluation (IPE) will be to address key questions of implementation and delivery including fidelity, dosage and quality, reach and responsiveness, acceptability as well as mechanisms of change, barriers and enablers to implementation and capacity and capability to implement.

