What appears to be the mechanisms of change and perceived outcomes of the systemic practice pilot model for practitioners and families?

Methods

Intervention group:

- Keyworker survey
- Family interviews
- Keyworker interviews and focus groups
- Systemic practitioner analysis of case files
- Observations of training and practice
- Keyworker and systemic practitioner case studies and learning log
- Administrative data on families and keyworkers

Barriers, Facilitators & Unintended Consequences

Main Question:

What are the challenges and enablers as well as unintended consequences to implementing the systemic practice pilot model?

Methods

Intervention group:

- Keyworker survey
- Family interviews
- Keyworker interviews and focus groups
- Systemic practitioner analysis of case files
- Observations of training and practice
- Keyworker and systemic practitioner case studies and learning log

- Administrative data on families and keyworkers

Capacity and Capability

Main Question:

What is the capability and capacity of local authorities to implement the systemic practice pilot model?

Methods

Intervention group:

- Keyworker survey
- Family interviews
- Keyworker interviews and focus groups
- Systemic practitioner analysis of case files
- Observations of training and practice
- Keyworker and systemic practitioner case studies and learning log
- Administrative data on families and keyworkers

Control group:

- Keyworker survey
- Administrative data on families and keyworkers

Unintended Outcomes

Main Question:

Are there any unintended outcomes as a result of implementation of systemic practice in keyworker teams?

Methods

Intervention group:

- Family interviews
- Keyworker interviews and focus groups
- Systemic practitioner analysis of case files
- Observations of training and practice
- Keyworker and systemic practitioner case studies and learning log
- Administrative data on families and keyworkers

IPE research methods

The IPE will include an extensive mixed-methods design, building on Foundation's feasibility and pilot studies and other studies looking at the implementation of systemic practice, including evaluations of the Reclaiming Social Work model.

In intervention local authorities the IPE will include:

1. Survey of keyworkers before training, post training and at the end of the pilot.

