- Participants / Data Sources: Practitioners from all 6 treatment and 4 control local authorities
- Data Analysis Methods: Quantitative analysis
- Research Questions Addressed:
 - Do keyworkers have increased levels of practice quality and professional wellbeing compared to practitioners in local authorities that have not implemented the model?

Interviews and Focus Groups

- Data Collection Methods: In-person or virtual interviews, recorded or notes taken
- Participants / Data Sources:
 - Focus groups with keyworkers in intervention local authorities (approximately 72 participants in total)
 - Focus groups with keyworkers in control local authorities (approximately 24 participants in total)

- Interviews with senior staff (team managers and heads of service) in intervention and control local authorities (10–20 participants in total)
- Interviews with systemic practitioners in intervention local authorities (6 participants in total)
- Data Analysis Methods: Qualitative thematic analysis
- Research Questions Addressed:
 - Do families have a better therapeutic alliance with their keyworker in local authorities that have implemented the systemic practice model compared to local authorities that have not?
 - Do keyworkers have increased levels of practice quality and professional wellbeing compared to practitioners in local authorities that have not implemented the model?
 - Are there any unintended outcomes as a result of implementation of the systemic practice model?

Observations

- Data Collection Methods: In-person observation of a training session, keyworker practice sessions, and sessions with families if feasible; note-taking
- Participants / Data Sources: Training sessions with keyworkers, reflective practice sessions with keyworkers, support sessions with families
- Data Analysis Methods: Qualitative analysis of observation notes
- Research Questions Addressed:
 - Do families have a better therapeutic alliance with their keyworker in local authorities that have implemented the systemic practice model compared to local authorities that have not?
 - Do keyworkers have increased levels of practice quality and professional wellbeing compared to practitioners in local authorities that have not implemented the model?

Casefile Analysis

- Data Collection Methods: Requesting a sample of keyworker casefiles
- Participants / Data Sources: Keyworkers and families
- Data Analysis Methods: Casefile analysis
- Research Questions Addressed:

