The evaluation will go through a full ethics application via our Research Ethics Committee (REC) chaired by [name]. An ethics application will be submitted to the REC and discussed at appropriate REC quarterly meetings. A minimum of two members of the REC will review the application. Possible outcomes of the review are favourable, conditionally favourable or unfavourable. A favourable decision means the project and evaluation can go ahead as proposed. If a conditionally favourable decision is made, the project and evaluation can only go ahead once certain conditions are met. If an unfavourable decision is made, the project and evaluation will need to be revised and then reconsidered by the REC.

The project and evaluation will not start until Coram's REC and DfE's ethics board have provided ethical approval.

A RCT design raises ethical questions about the control local authorities being denied systemic practice. However, as systemic practice is not part of usual support offered to families as part of the Supporting Families Programme, those in the control group are not being denied a service that they would have otherwise received. In addition, as there have been no previous impact studies of systemic practice in early help, it is unclear if it is effective in supporting keyworkers to help families achieve better outcomes for themselves. A well-planned and executed pilot RCT would be more likely to provide causal evidence of impact than other forms of evaluation such as a quasi-experimental design (QED).

To minimise ethical issues (and as is typical of trials in family support), the RCT will be unblinded. Local authorities, keyworkers and families will know or be able to find out that they are in a pilot RCT and that they are in the control or intervention group.

We do not anticipate either families or keyworkers will experience harm as a result of participation, but we would gather information through regular communication with local authorities and IFT about any emerging risks and harms. If evidence emerged of serious and substantial harms being caused to families in either the control or intervention group, we would consult Coram's REC. Ethically, we feel it is important that the evaluation is co-designed with CYP. Therefore, we will work with our peer researcher young advisors in throughout the evaluation to ensure our design, data collection, analysis and dissemination is informed by them.

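### Harm ascertainment is unequal between arms and inconsistently described, so a comparison of informally reported harms would be open to bias of unknown direction

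*Protocol*

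**What the plan says.** **Collection of harms.** Under Ethics, the evaluators state that "we would gather information through regular communication with local authorities and IFT about any emerging risks and harms". No form, definition or schedule by arm is given there. The REC would be consulted about "serious and substantial harms being caused to families in either the control or intervention group", so the escalation rule covers both arms.

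**Planned use.** The Analysis section of the impact evaluation says: "The analysis will also include an exploratory analysis with sub-groups or other exploratory analysis including analysis of harms". It names no data source and no comparison. Under Feasibility for a full-scale trial, unintended consequences found by the IPE also inform whether to proceed.

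**Unintended outcomes in the IPE.** Under the heading Unintended Outcomes the question is "Are there any unintended outcomes as a result of implementation of systemic practice in keyworker teams", and every method listed belongs to the intervention group. The same holds for the question "What are the challenges and enablers as well as unintended consequences to implementing the systemic practice pilot model". The later overview of IPE methods and Table 12 instead place the unintended-outcomes question under interviews and focus groups, whose participants include control keyworkers and control senior staff.

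**Who works where.** IFT's delivery lead works across the intervention LAs, and each systemic practitioner there has "monthly clinical supervision with IFT's Systemic Psychotherapist Delivery Lead" as well as a monthly group meeting run by the same lead. IFT trains control LAs at the end of pilot delivery, which Annex A dates to May 2026. The Recruitment and Practitioner surveys sections, as worded, also give systemic practitioners a role in control LAs.

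**The concern.** A harm can be counted only if someone asks about it or hears of it. One of the two named sources, IFT, is in regular contact with intervention LAs and has no scheduled contact with control LAs while families are being followed. If events from both sources were put into one count and compared by arm, a difference could reflect how the events were found. A false excess could be reported, or a real excess dismissed as an artefact of closer contact.

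The REC question does not depend on any comparison. The escalation rule promises equal attention to both arms, but the control arm has fewer named routes by which an event would come to light.

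This is a matter of data collection and not only of analysis detail that may sit in the SAP. No later analysis can recover control-arm harms that nobody asked about.

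**Working it through.** The protocol gives no harm rate, detection rate or harm sample size, so there is no figure to reproduce. The check sets the sections side by side.

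**1. Routes by arm**

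| Route | Intervention | Control | Where stated |
|---|---|---|---|
| Communication with LAs | Yes | Yes | Ethics |
| Evaluation-team support to LAs | Yes | Yes | Recruitment; Incentives for control local authorities |
| IFT during family follow-up | Yes | No; training in May 2026 | Systemic practice pilot; Annex A |
| Keyworker focus groups | about 72 people | about 24 people | Keyworker focus groups and interviews |
| Senior-staff interviews | Mid-study and near the end | Once, near the end | same |
| Family interviews | 18 | none listed | Interviews with families |
| Keyworker-family session observations, if feasible | 18 | none listed | Observations |

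Annex A ends midline and endline family data collection at the end of April 2026, so IFT's control training falls after it. For scale, six practitioners with monthly supervision over the 12 to 15 months in Table 10 is 6 × 12 = 72 to 6 × 15 = 90 supervision contacts, with no control counterpart. The protocol does not say that these meetings pass case-level harms to the evaluators.

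**2. Consistency of the IPE text**

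- The Unintended Outcomes list has six intervention-group methods and no control entry.
- Programme Differentiation and Capacity and Capability do carry control entries (keyworker survey and administrative data), so the layout allows for them.
- The IPE analysis overview and Table 12 assign the unintended-outcomes question to a method whose sources include "Focus groups with keyworkers in control local authorities (approximately 24 participants in total" and senior staff in both arms.

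These descriptions disagree.

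**3. Consistency on systemic practitioners**

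The sections on the pilot and on local authority systemic practitioners place them in intervention LAs, and the Virtual Hub section speaks of six hired practitioners. Recruitment, speaking of keyworkers in both arms, mentions support from their LA's systemic practitioner. Practitioner surveys has the practitioner promoting the endline survey in both arms. These also disagree.

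**4. Direction, on assumed values only**

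Let true harm be equal in the two arms. Let s be the share of harms found through LAs, a the share of the remainder found through intervention-only routes, and d the relative loss of LA reporting in the intervention arm. Then

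recorded ratio (intervention : control) = [s(1 − d) + a(1 − s(1 − d))] / s

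| s | a | d | Calculation | Ratio |
|---|---|---|---|---|
| 0.7 | 0.1 | 0 | (0.70 + 0.03) / 0.70 | 1.04 |
| 0.5 | 0.2 | 0 | (0.50 + 0.10) / 0.50 | 1.20 |
| 0.3 | 0.5 | 0 | (0.30 + 0.35) / 0.30 | 2.17 |
| 0.5 | 0.1 | 0.3 | (0.35 + 0.065) / 0.50 | 0.83 |

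None of s, a or d comes from the documents. The table shows only that the ratio can move away from 1 in either direction with no true difference.

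**The case against.** **No comparison of informal reports is stated.** The Ethics text is monitoring that prompts consultation of the REC, and the planned analysis of harms names no source. This stands. The bias is conditional on informal reports being compared by arm. A reader might infer that every between-arm harm comparison is compromised, but the documents do not support that: step-up to statutory services (Table 6) and the Family Outcome Questionnaire are collected by the same routes in both arms.

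**Controls are not left out.** A reader of the Unintended Outcomes list alone might infer that the question is pursued only in the intervention arm. The analysis overview and Table 12 contradict that reading. What remains is an inconsistency and an imbalance, with no control families interviewed.

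**The IPE question concerns effects of implementation.** Controls do not implement the model, so a focus on the intervention arm is natural for that question. This is fair for the IPE but does not extend to the harm monitoring, which is promised for both arms.

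**Direction is not shown.** It is tempting to conclude that extra contact biases results against the intervention. But IFT delivers the model and reporting is unblinded, so under-reporting is equally possible, and the last row above reverses the sign.

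**Some extra routes may find little.** Session observations depend on feasibility, case files are to hold only practice and process information, and 18 interviews are about 5% of the 361 analysable intervention families (18 / 361). Control LAs have continuing evaluation-team support, and safeguarding escalation is not restricted by arm. All of this limits the likely size, but it does not make the routes equal.

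**Conclusion.** The point holds in a limited form. Harm ascertainment is unequal by design, because one of the two named sources reaches only the intervention arm during family follow-up, and the protocol describes the collection of unintended outcomes in two ways that disagree. A between-arm comparison using informally reported harms would be open to ascertainment bias of unknown direction and size. Harm in control families has fewer named routes to the REC; how many events would be missed as a result cannot be estimated from the documents.

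The illustrative ratios (1.04 to 2.17 with equal LA reporting, 0.83 with reduced LA reporting in the intervention arm) rest wholly on assumed detection rates and predict nothing. Comparisons on step-up or on the questionnaire do not have this fault. The change is worth making because it is cheap and has to be made during data collection.

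**What to change.** 1. Send one identical, regular harms query to all ten LAs through the contact that the evaluation team already has, with the same wording and interval in both arms.
2. Limit between-arm harm comparison to data collected the same way in both arms: that query, step-up to statutory services, and worsening on the Family Outcome Questionnaire. Do not treat 2.45 GBO points as a harm threshold. The protocol reports it as a meaningful-change level, and on the adult 1 to 10 scale a goal rated 3 at baseline can fall by at most 3 − 1 = 2.
3. Report events learned through IFT, systemic practitioners or intervention-only IPE methods separately and descriptively. This separation concerns comparative counts only; such events still go to the REC where the Ethics section calls for it.
4. Reconcile the Unintended Outcomes list with the IPE analysis overview and Table 12. Reconcile the sections placing systemic practitioners in intervention LAs with Recruitment and Practitioner surveys.

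The cost is protocol and SAP wording plus a few minutes per LA per query. An identical query does not remove the effect of unblinded reporting, which should be stated as a limitation.

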Annex A – High-level timeline

Systemic practice pilot timeline

August 2024

- MOU and DSA signed — *Coram*

September 2024

- Ethical approval given — *Coram*

October 2024 – April 2025

- Pilot starts: IFT training (1-day intro for all staff and 5 days training for all keyworkers) — *IFT / Local Authorities*

November 2024 – April 2025

- Pre-training survey of keyworkers — *Ecorys / Coram*

January 2025

- Start of outcome data collection with families by keyworkers — *Local Authorities*
- Drop-in sessions for keyworkers and LA staff working on the Pilot begin — *Coram*
- IPE and qualitative data collection (interviews, observations) begins — *Coram*

April – June 2025

- Post-training survey of keyworkers — *Ecorys / Coram*

April – October 2025

- Additional 10 days training for identified ‘systemic champion’ keyworkers — *IFT*

February 2026

- End of baseline outcome data collection with families by keyworkers — *Local Authorities*

End April 2026

- End of midline and endline outcome data collection with families by keyworkers — *Local Authorities*

April – May 2026

- Post-pilot survey of keyworkers — *Ecorys / Coram*

May 2026

- Outcome data matching with LA data on families — *Local Authorities / Coram*
- Control group local authorities receive training — *IFT*

End May 2026

- Final administrative data to Coram — *Local Authorities / IFT*

June 2026

- Coram data clean and QA — *Coram*

August 2026

- IPE and outcome data analysis — *Coram*

Autumn 2026

- Draft final report to DfE — *Coram*
- Final published report — *DfE*

Annex B – Family outcomes questionnaires

Systemic Practice Pilot Family Outcomes Questionnaire

ADULT QUESTIONNAIRE – PAPER VERSION

This is a paper copy of the Family Outcomes Questionnaire for **adult** family members as part of the Systemic Practice Pilot Study. We are using this questionnaire to support the evaluation of the pilot.

Please also take a paper copy of the privacy notice to give to parent/carers and children **before** they consent to completing the questionnaire: <https://www.coram.org.uk/wp-content/uploads/2024/11/Systemic-Practice-DPN-parents-carers-and-children-FINAL.pdf>

Information collected on this paper version should be uploaded via the link: <https://www.smartsurvey.co.uk/s/FamilyOutcomeQuestionnaire/>

Administrative information for the Keyworker to complete

Please write the local authority ID number for the adult completing the questionnaire. The ID will be the one you use in your service for the adult or family.

Providing this is very important as it will allow us to use the questionnaire data in the pilot.

Adult/family ID

1. Please tick the box to indicate who is completing this questionnaire.

| | |
|---|---|
|  Mother |  Father |
|  Other carer/guardian |  Other adults in the household/family (for example, step parent) (e.g. grandparent, older sibling etc.) |

2. Has this family member completed the questionnaire before?

No, this is their first time completing the questionnaire

- Yes, they have completed the questionnaire before, and today they are completing it as part of a review of their progress
- Yes, they have completed the questionnaire before, and they are completing it as part of ending our support (case closure)

3. Please state roughly how long you have worked with the family. If the family have been re-referred, please state how long you have been working with them since the rereferral.

| | |
|---|---|
|  Less than a week |  9 to 12 weeks |
|  1 to 2 weeks |  3 to 6 months |
|  3 to 4 weeks |  7 to 12 months |
|  5 to 8 weeks |  Over 12 months |

Introduction

Thank you for agreeing to complete the Family Outcomes Questionnaire.

The questionnaire will ask a series of questions divided into three sections. They will cover:

- **Your family** – 15 questions about how you see your family at the moment.
- **Your goals** – goals (up to three) you want to achieve for your family through this service. It also asks your views on your current progress towards these goals.
- **Your keyworker** – 10 questions about your relationship with your keyworker.

If you have any questions when completing the questionnaire **please ask your keyworker and they will be able to help you.**

Section 1: Your Family

In this section we would like you to tell us about how you see your family at the moment. **So we are asking for your view of your family.** When people say 'your family' they often mean the people who live in your house. **But we want you to choose who you want to count as the family you are going to describe.**

There are 15 short questions. Please tick whether the statement describes your family very well through to not well at all. For example, if a statement was "We are always fighting each other" and you felt this was not especially true of your family, you would tick the box that says "Describes us: not well".

Very Well / Well/ / Partly / Not very well / Not at all

X

Do not think for too long about any question, but do try to tick one of the boxes for each question.

For each line, would you say **this describes our family**: Very well / Well / Partly / Not very well / Not at all / Do not want to answer

1. In my family we talk to each other about things which matter to us
2. People often don't tell each other the truth in my family
3. Each of us gets listened to in our family
4. It feels risky to disagree in our family
5. We find it hard to deal with everyday problems
6. We trust each other
7. It feels miserable in our family
8. When people in my family get angry they ignore each other on purpose
9. We seem to go from one crisis to another in my family
10. When one of us is upset they get looked after within the family
11. Things always seem to go wrong for my family

12. People in the family are nasty to each other
13. People in my family interfere too much in each other's lives
14. In my family we blame each other when things go wrong
15. We are good at finding new ways to deal with things that are difficult

Section 2: Your Goals

In this section we want to know the most important **goals** to you that you want to achieve for your family in coming to this service.

We will ask you to list up to **three** of your goals. After each goal we will ask how close you feel you are currently in progress to reaching that goal on a scale from zero to ten. A score of zero means no progress has been made towards a goal, a score of ten means a goal has been reached fully, and a score of five is exactly half way between the two.

Your first goal is:

How close do you feel to reaching your first goal?

- 1 – Goal not at all met
- 2
- 3
- 4
- 5 – Half way to reaching goal
- 6
- 7
- 8
- 9
- 10 – Goal reached

Your second goal is:

How close do you feel to reaching your second goal?

- 1 – Goal not at all met
- 2
- 3
- 4
- 5 – Half way to reaching goal
- 6
- 7
- 8
- 9
- 10 – Goal reached

Your third goal is:

How close do you feel to reaching your third goal?

1 – Goal not at all met

2

3

4

5 – Half way to reaching goal

6

7

8

9

10 – Goal reached

Section 3: Your Keyworker

This section asks 10 questions about working with your keyworker present here today.

For this section, you **do not need to discuss** your answers with your keyworker. Instead, please give your honest opinion on the support you have been given. Please note, answers given here or anywhere in this questionnaire **will not affect the support you receive from this service** in any way.

For each line, would you say **this describes your relationship with your keyworker**:
Poor / Fair / Good / Very good / Excellent / Does not apply / Do not want to answer

1. **Making you feel at ease** (*introducing him/herself, explaining his/her position, being friendly and war towards you, treating you with respect, not cold or abrupt*)
2. **Letting you tell your "story"** (*giving you time to fully describe your condition in your own words; not interrupting, rushing, or diverting you*)
3. **Really listening** (*paying close attention to what you were saying; not looking at the notes or computer as you were talking*)
4. **Being interested in you as a whole person** (*asking/knowing relevant details about your life or your situation; not treating you as 'just a number'*)
5. **Fully understanding your concerns** (*communicating that he/she had accurately understood your concerns and anxieties; not overlooking or dismissing anything*)
6. **Showing care and compassion** (*seeming genuinely concerned, connecting with you on a human level; not being indifferent or 'detached'*)
7. **Being positive** (*having a positive approach and a positive attitude; being honest but not negative about your problems*)

8. **Explaining things clearly** (*fully answering your questions, explaining clearly, giving you adequate information; not being vague*)
9. **Helping you to take control** (*exploring with you about what you can do to improve your health yourself; encouraging rather than 'lecturing' you*)
10. **Making a plan of action with you** (*discussing the options, involving you in decisions as much as you want to be involved; not ignoring your views*)

Thank you for completing this questionnaire, it is an important part of the pilot.

For further information on how this information will be used, please see the **Date Privacy Notice**: <https://www.coram.org.uk/wp-content/uploads/2024/11/Systemic-Practice-DPN-parents-carers-and-children-FINAL.pdf>

Systemic Practice Pilot Family Outcomes Questionnaire

CHILD (8-17 years old) QUESTIONNAIRE – PAPER VERSION

This is a paper copy of the Family Outcomes Questionnaire for **child (aged 8 and over)** family members as part of the Systemic Practice Pilot Study. We are using this questionnaire to support the evaluation of the pilot.

Please also take a paper copy of the privacy notice to give to parent/carers and children **before** they consent to completing the questionnaire: <https://www.coram.org.uk/wp-content/uploads/2024/11/Systemic-Practice-DPN-parents-carers-and-children-FINAL.pdf>

Information collected on this paper version should be uploaded via the link: <https://www.smartsurvey.co.uk/s/FamilyOutcomeQuestionnaire/>

Administrative information for the Keyworker to complete

1. **Please write the local authority ID number for the child completing the questionnaire. The ID will be the one you use in your service for the child.**

Providing this is very important as it will allow us to use the questionnaire data in the pilot.

2. **Child ID**

Has this child completed the questionnaire before?

- No, this is their first time completing the questionnaire
- Yes, they have completed the questionnaire before, and today they are completing it as part of a review of their progress
- Yes, they have completed the questionnaire before, and they are completing it as part of ending our support (case closure)

3. Please state roughly how long you have worked with the child. If the child have been re-referred, please state how long you have been working with them since the rereferral.

- Less than a week 9 to 12 weeks
- 1 to 2 weeks 3 to 6 months
- 3 to 4 weeks 7 to 12 months
- 5 to 8 weeks Over 12 months

Introduction

Thank you for agreeing to fill in this questionnaire.

The questions will cover:

- **Your family** –15 questions about how you see your family at the moment.
- **Your goals** –goals (up to three) you want to achieve for your family through this service. It also asks about your progress towards these goals.
- **Your keyworker** –10 questions about your relationship with your keyworker.

If you have any questions when completing the questionnaire **please ask your keyworker and they will be able to help you.**

Section 1: Your Family

In this section we would like you to tell us about how you see your family at the moment. **So we are asking for your view of your family.** When people say 'your family' they often mean the people who live in your house. **But we want you to choose who you want to count as the family you are going to describe.**

There are 15 short questions. Please tick whether the statement describes your family very well through to not well at all. For example, if a statement was "We are always

fighting each other" and you felt this was not especially true of your family, you would tick the box that says "Describes us: not well".

Very Well / Well/ / Partly / Not very well / Not at all

X

Do not think for too long about any question, but do try to tick one of the boxes for each question.

For each line, would you say **this describes our family**: Very well / Well / Partly / Not very well / Not at all / Do not want to answer

1. In my family we talk to each other about things which matter to us
2. People often don't tell each other the truth in my family
3. Each of us gets listened to in our family
4. It feels risky to disagree in our family
5. We find it hard to deal with everyday problems
6. We trust each other
7. It feels miserable in our family
8. When people in my family get angry they ignore each other on purpose
9. We seem to go from one crisis to another in my family
10. When one of us is upset they get looked after within the family
11. Things always seem to go wrong for my family
12. People in the family are nasty to each other
13. People in my family interfere too much in each other's lives
14. In my family we blame each other when things go wrong
15. We are good at finding new ways to deal with things that are difficult

Section 2: Your Goals

In this section we want to know the most important **goals** to you that you want to achieve for your family in coming to this service.

We will ask you to list up to **three** of your goals. After each goal we will ask how close you feel you are currently in progress to reaching that goal on a scale from zero to ten. A score of zero means no progress has been made towards a goal, a score of ten means a goal has been reached fully, and a score of five is exactly half way between the two.

In coming to our service today, what are some of the goals you want to achieve?

Goal 1

Our Goal is:

.....
Made by:

How close are you to reaching this goal?

0 1 2 3 4 5 6 7 8 9 10

Not at all close

Halfway

Goal reached!

Goal 2

Our Goal is:

.....
Made by:

How close are you to reaching this goal?

0 1 2 3 4 5 6 7 8 9 10

Not at all close

Halfway

Goal reached!

Goal 3

Our Goal is:

.....
Made by:

How close are you to reaching this goal?

0 1 2 3 4 5 6 7 8 9 10

Not at all close

[figure not shown]
[figure not shown]
[figure not shown]
[figure not shown]
[figure not shown]
[figure not shown]
Halfway

[figure not shown]
[figure not shown]
Goal reached!

Section 3: Your Keyworker

This section asks 10 questions about working with your keyworker present here today.

For this section, you **do not need to discuss** your answers with your keyworker. Instead, please give your honest opinion on the support you have been given. Please note, answers given here or anywhere in this questionnaire **will not affect the support you receive from this service** in any way.

| | | | | | | |
|---|---|---|--|---|---|---|
|  | 1... making you feel at ease? (being friendly and warm towards you) | | | | | |
| | poor | fair | good | very good | excellent | does not apply |
| |  |  |  |  |  |  |
|  | 2... letting you tell your 'story'? (giving you time to fully describe things in your own words) | | | | | |
| | poor | fair | good | very good | excellent | does not apply |
| |  |  |  |  |  |  |
|  | 3... really listening? (paying close attention to what you are saying) | | | | | |
| | poor | fair | good | very good | excellent | does not apply |
| |  |  |  |  |  |  |
|  | 4... being interested in you as a whole person? (asking/knowing relevant details about your life, your situation) | | | | | |
| | poor | fair | good | very good | excellent | does not apply |
| |  |  |  |  |  |  |
|  | 5... fully understanding your concerns? (communicating that s/he had accurately understood your problems) | | | | | |
| | poor | fair | good | very good | excellent | does not apply |
| |  |  |  |  |  |  |

| | | | | | | |
|--|--|--|--|--|--|--|
|  | 6... showing care and compassion? (seeming genuinely concerned) | | | | | |
|  | | | | | | |
|  | 7... being positive? (having a positive approach and positive attitude) | | | | | |
|  | | | | | | |
|  | 8... explaining things clearly? (fully answering your questions, giving you enough information) | | | | | |
|  | | | | | | |
|  | 9... helping you to take control? (exploring with you what you can do to improve your health yourself) | | | | | |
|  | | | | | | |
|  | 10... making a plan of action? (discussing the options, involving you as much as you want) | | | | | |
|  | | | | | | |
| If you would like to explain any of your responses, please use this space or overleaf. | | | | | | |

Thank you for completing this questionnaire, it is an important part of the pilot.

For further information on how this information will be used, please see the **Date Privacy Notice**: <https://www.coram.org.uk/wp-content/uploads/2024/11/Systemic-Practice-DPN-parents-carers-and-children-FINAL.pdf>

© Department for Education copyright 2025

This publication is licensed under the terms of the Open Government Licence v3.0, except where otherwise stated. To view this licence, visit nationalarchives.gov.uk/doc/open-government-licence/version/3.

Where we have identified any third-party copyright information you will need to obtain permission from the copyright holders concerned.

Reference: RR1577

ISBN: 978-1-83870-736-1

For any enquiries regarding this publication, contact www.gov.uk/contact-dfe.

This document is available for download at www.gov.uk/government/publications.
